### 10.1.6 Relationship to Study Procedures

The relationship should be assessed as Related if the investigator considers that there is reasonable possibility that an event is due to a study procedure. Otherwise, the relationship should be assessed as Not Related.

### 10.1.7 Study Date

The start date of AEs will be determined using the following criteria.

AE	Start date
Signs, symptoms, diseases (diagnoses)	The date on which the first signs/symptoms were noted by the subject and/or the investigator.
Asymptomatic diseases	The date on which a diagnosis was confirmed through a test(s). The date on which a diagnosis was confirmed, even when the test results indicate an old sign(s) of the disease or an approximate time of its onset.
Exacerbation of comorbidities	The date on which the first worsening of diseases/symptoms was noted by the subject and/or the investigator.

Onset of a test abnormality after the start of study drug administration	The date on which a clinically significant laboratory abnormality was detected.
Worsening of a baseline test abnormality after the start of study drug administration	The date on which a clear increase/decrease in a laboratory parameter was clinically confirmed based on the time profile of the parameter.

### 10.1.8 Stop Date

The stop date of the AE is the date at which the subject recovered, the event resolved but with sequelae or the subject died. The AE will be recorded as “ongoing” if the subject has not yet recovered by the end of the study.

### 10.1.9 Action Concerning Study Drug

Action concerning study drug will be classified or defined as shown below.

Drug withdrawn	The study drug is discontinued because of an AE (including withdrawal by the subject at his/her discretion). If the study drug is continued after the study termination, the action should be “Dose not changed”.
Dose not changed	The dose was not changed after the onset of the AE. The study drug was discontinued, reduced, or increased because of another AE. The study drug was discontinued or reduced for a reason other than the AE, e.g., inadvertence of the subject.
Unknown	It has not been possible to determine what action has been taken because the subject is lost to follow-up.
Not Applicable	The administration of the study drug had already been completed or discontinued before the onset of the AE.
Dose reduced	The dose of the study drug was reduced because of the AE (including dose reduction by the subject at his/her discretion).
Dose Increased	The dose was increased due to the particular AE (including dose reduction by the subject at his/her discretion).
Washout	The study drug was suspended (i.e., interrupted) because of the AE (including suspension/interruption by the subject at his/her discretion), but resumed later.

### 10.1.10 Outcome

Outcome of AEs is classified as follows:

Category	Criteria
Recovered	Disappearance or recovery of symptoms and findings

	Laboratory values returned to normal or baseline
Improved	The intensity is lowered by one or more stages Symptoms or findings mostly disappeared Laboratory values improved, but have not returned to normal or baseline The subject died from a cause other than the concerned AE while the condition was resolving (recording of the date of death unnecessary)
Not recovered	No change in symptoms, findings, or laboratory data The symptoms, findings, or laboratory data on the final day of observable period were aggravated compared with the date of onset Irreversible congenital anomaly The subject died from another cause before resolution of the concerned AE (recording of the date of death unnecessary)
Recovered with sequelae	Disability that disturbs daily life
Death	Direct relationship between death and the concerned AE “Direct relationship” means that the concerned AE was the cause of death, or the concerned AE was clearly responsible for death. Outcome of an AE which was not determined (judged, presumed) a direct cause of death observed in the same subject is not considered as death. The date of death shall be recorded.
Unknown	Follow-up specified in the protocol after the date of onset was not possible due to change of hospitals or relocation, etc.

## 10.2 Procedures

### 10.2.1 Collection and Reporting of AEs

#### 10.2.1.1 AE collection Period

Collection of AEs will commence from the time that the subject is first administered study drug (VISIT 1). Routine collection of AEs will continue until VISIT 3.

#### 10.2.1.2 AE Reporting

At each study visit, the investigator will assess whether any subjective AEs have occurred. A neutral question, such as “How have you been feeling since your last visit?”. Subjects may report AEs occurring at any other time during the study.

All subjects experiencing AEs, whether considered associated with the use of the study drug or not, must be monitored until the symptoms subside and any clinically relevant changes in laboratory values have returned to baseline or until there is a satisfactory explanation for the changes observed. All AEs will be documented in the AE page of the CRF, whether or not the investigator concludes

that the event is related to the drug treatment. The following information will be documented for each event:

1. Event term.
2. Start and stop date.
3. Frequency.
4. Intensity.
5. Investigator's opinion of the causal relationship between the event and administration of the study drug (related or not related),
6. Investigator's opinion of the causal relationship to study procedures, including the detail of the suspected procedure.
7. Action concerning study drug.
8. Outcome of event.
9. Seriousness.

#### **10.2.1.3 Reporting of adverse events of special interest (specific adverse events)**

If AE of Special interest (AESI) occurring during the AE collection period is considered to be clinically significant based on the criteria below, it should be reported to the sponsor (refer to the attachment for contact information) within 1 business day of first onset, or subject's notification of the event by the investigators. AESI Form should be completed and signed (or signed and sealed) by the principal investigator and reported to the sponsor within 10 business days.

The criteria for AESIs (hypoglycemia-related AEs, intestinal obstruction-related AEs, acute pancreatitis-related AEs, and QT/QTc interval prolongation-related AEs) are as shown below. If any other AEs potentially related to the study drug occur, it will be considered whether to include them in the AESIs.

[Hypoglycemia-related AEs]

AEs related to hypoglycemia

[Intestinal obstruction-related AEs]

Intestinal obstruction, ileus, subileus, obstruction of the digestive tract, gastrointestinal motility disorder, impaired gastric emptying, and AEs related to these conditions

[Acute pancreatitis-related AEs]

AEs related to pancreatitis or acute pancreatitis

[QT/QTc interval prolongation-related AEs]

Torsade de pointes, sudden death, ventricular tachycardia, ventricular fibrillation, ventricular flutter, consciousness disturbed, convulsion, ECG QT prolonged, and AEs related to these conditions

[Liver dysfunction or jaundice-related AEs]

AEs corresponding to 'Liver dysfunction related to drug - comprehensive search' in MedDRA standard search formula.

The AESIs have to be recorded as AEs in the CRF. A report along with all other required documentation must be submitted to the sponsor.

### **10.2.2 Collection and Reporting of SAEs**

When a SAE occurs through the AE collection period it should be reported according to the following procedure:

At the time of onset of a SAE or notification of the onset by the subject, the principal investigator shall report the SAE to the chief executive of the study site immediately, and the sponsor or the contract study organization (CRO) to whom the sponsor has entrusted responsibility shall notify the principal investigator of the study site.

A SAE should be reported by the investigator to the sponsor within 1 business day of the SAE occurrence. The investigator should submit the detailed SAE Form to the sponsor (for contact information, refer ) within 10 calendar days. .

Furthermore, it shall be mandatory to include the contents below in the report to be submitted to the sponsor within 1 working day, and other items shall be reported as far as possible.

- A short description of the event and the reason for why the event is categorized as serious.
- Study title.
- Subject identification number.
- Study site's name.
- Investigator's name.
- Name of the study drug.
- Causality assessment.

The investigator shall report spontaneously reported SAEs that are collected even after the AE collection period to the sponsor.

### **10.2.3 Reporting of Additional Information Concerning AEs**

If the sponsor requests provision of additional information concerning AEs for reporting to regulatory authorities, the investigators shall confirm the necessary additional information and enter in the electronic data capture (EDC) system or submit a report within the period specified by the sponsor.

### **10.3 Follow-up of SAEs**

If information not available at the time of the first report becomes available at a later date, the investigator should complete a follow-up SAE form (copy) or provide other written documentation

and submit it to the sponsor (for contact information, refer ) within 1 working day. Relevant data collected at the study site (e.g., ECG charts, laboratory test values, discharge summary, postmortem results) shall be sent to the sponsor or the committee such as the ethics review committee upon request.

All SAEs should be followed up until resolution or permanent outcome of the event.

### **10.3.1 Reporting of SAEs, etc., to IECs, etc., and Regulatory Authorities**

When the chief executive of study site receives a report of a SAE from the principal investigator, the chief executive of study site shall consult the Ethical Review Board, etc., and notify the study sites that are conducting the study through the sponsor or the CRO consigned by the sponsor.

When the principal investigator reported a SAE for which a causal relationship to the study (study drug or comparative drug) cannot be ruled out and is unexpected, the chief executive of the study site shall prepare a written report of the unexpected SAE containing the information reported by the principal investigator plus the information below, and submit the report to the Minister of Health, Labour and Welfare, and notify other study sites conducting the study. (The chief executive of the study site may report it to the Minister of Health, Labour and Welfare via the sponsor, and notify it to other study sites via the sponsor.)

- Actions taken for SAEs  
(discontinuation of new enrollment, revision of informed consent form, re-consents from other subjects, etc.)
- Date of review, summary of review, result, necessary action, etc., related to Ethics Review Committee, etc.
- Notification to other study sites

The sponsor shall report, in accordance with regulations, unexpected serious adverse drug reactions and other SAEs that are subject to emergency reporting to regulatory authorities, the investigators, and chief executives of study sites.

From the time point of first acknowledging the event or receiving additional information, the sponsor or the CRO consigned by the sponsor shall comply with regulatory required time frames for reporting, and make emergency reports concerning unexpected serious adverse drug reactions and expected serious adverse drug reactions to regulatory authorities. Also, the sponsor shall, in the same way, make an emergency report of other critical safety information that may have a major effect on the risks/benefits of the study drug, continuation of study drug administration, or continuation of study. The study site shall submit copies of emergency report documents to the Ethics Review Committee, etc.

## **11.0 STUDY-SPECIFIC COMMITTEES**

### **11.1 Steering Committee**

The Steering Committee will comprise of the chair and the sponsor. The Steering Committee will supervise implementation and reporting of the study, secure medical guidance of a high degree of professionalism and a high-level scientific quality, and revise the protocol appropriately. The responsibilities of the committee will be described in the procedures of the Steering Committee.

## **12.0 DATA HANDLING AND RECORDKEEPING**

Data Management department of the sponsor shall be in charge of implementing data management operation according to the standard operating procedures, independently from Medical Affairs department. AEs, and concurrent conditions shall be coded using MedDRA. Drugs shall be translated using the World Health Organization (WHO) Drug Dictionary.

### **12.1 Case Report Forms (CRFs)**

Completed CRFs are required for each subject who signs informed consent.

The sponsor or its designee will provide study sites with access authorization to the EDC system. Before use of the EDC system, the sponsor shall provide training to the investigators, and study collaborators. The CRF shall be used to report the information collected during the study period to the sponsor. The CRF shall be prepared in Japanese. Data shall be directly entered in preparing the CRF.

A change or correction of the CRF shall be recorded as an audit trail that records the information before and after the change or correction, the person who made the change or correction, date of change or correction, and its reason.

The principal investigator or its designee shall ensure the accuracy and completeness of the CRF, and provide an electronic signature on the relevant page of the CRF. The principal investigator bear full responsibility for the accuracy and reliability of all the data entered on the CRF.

The following data shall be recorded on the CRF directly, except for those recorded in the source documents:

- Eligibility, completion status, reason for discontinuation, seriousness of adverse events, severity of adverse events, and causal relationship between adverse events and the study drugs or the study procedures, and outcome

When the investigators make a change or correction in the data entered on the CRF after fixation of clinical data base, a record (Data Clarification Form) of change or correction on the CRF provided by the sponsor shall be used. The principal investigator shall confirm that the record of change or correction on the CRF is accurate and complete, and sign or write name/ affix a seal, and date it. The sponsor or the designee shall confirm that the CRF has been made appropriately in conformity with the procedure defined for each study. The sponsor or its designee shall have access to the medical records of the subjects and in-house records to ensure the accuracy of the CRF as necessary. The completed CRF shall be the property of the sponsor, and the investigator shall not disclose the information to a third party without written permission from the sponsor.

## **12.2 Timing of Data Entry into the EDC System**

The sponsor or its designee shall request the investigators to promptly enter data into the EDC system following enrollment of the subject, each visit during study treatment, and completion/discontinuation of the study.

## **12.3 Storage and Disposal of Specimens and Documents, etc.**

The principal investigator or the chief executive of the study site shall store human-derived specimens and the following materials (information, etc.), including those specified in Section 12.1 and study-specific documents to be used by the regulatory authority and the sponsor or its designee for investigation and audit. The documents shall include, but shall not be limited to the materials related to the information used in the study such as the subject ID number list, subjects' medical records, study work sheet, original signed and dated informed consent forms, an electronic copy of the EDC system with audit trails, and the drug management records. The principal investigator and the chief executive of the study site shall appropriately retain the specimens/information related to this study for at least 5 years from the date of reporting the end of the study by the principal investigator, or for 3 years from the date of reporting final publication of the study result, whichever date is later. However, when the sponsor requires a longer storage period, the chief executive of the study site shall discuss the period and methods of storage with the sponsor. When disposing the specimens, documents, etc., the chief executive of the study site shall dispose them anonymously.

## 13.0 STATISTICAL METHODS

The person in charge of analysis and the designee [analysis personnel, who belongs to CRO independent from the sponsor] shall perform the statistical analysis. The sponsor will not be involved in the statistical analysis.

### 13.1 Statistical and Analytical Plans

The person in charge of analysis shall prepare a statistical analysis plan (SAP) before the acquisition of the informed consent of the earliest subject, and issue the first edition. Detailed definition of endpoints and analysis methods should be specified in the SAP to deal with all the purposes of the study.

#### 13.1.1 Analysis Sets

In this study, two analysis sets comprising the “Full Analysis Set (FAS)” and the “Safety Population” will be established. The FAS used as the main efficacy analysis set is defined as “randomized subjects who receive at least one dose of study drugs”. The safety population is defined as “subjects who receive at least 1 dose of study drugs”.

#### 13.1.2 Analysis of Demographics and Other Baseline Characteristics

Using FAS, major demographic and other baseline characteristics shall be aggregated.

#### 13.1.3 Efficacy Analysis

The primary endpoint for this study is patient preference for treatment interviewed from the subjects using the standardized questions\* at the end of treatment period (treatment selection rate)

\*: Questions

Regarding the drug therapy after the end of this research, which treatment do you select from the following choices from 1 to 4?

1. Either once-weekly DPP-4 inhibitor or daily DPP-4 inhibitor
2. Once-weekly DPP-4 inhibitor
3. Daily DPP-4 inhibitor
4. Neither once-weekly DPP-4 inhibitor nor daily DPP-4 inhibitor

Among the subjects who were randomized and treated with the study drugs, the treatment selection rate will be calculated by merging the subjects from whom preference for treatment was interviewed by treatment group with the treatment groups. Also, the treatment selection rates for once-weekly DPP-4 inhibitor and daily DPP-4 inhibitor are compared by applying the Mainland-Gart test.

The secondary endpoints:

- Preference for treatment (treatment selection rate) by drug (trelagliptin or alogliptin) selected by subjects at the end of treatment period and by background factor

### 13.1.4 Safety Analysis

- Incidence of AEs (TEAEs)

[Analytical methods]

A treatment-emergent AE (TEAE) is defined as any AE occurring after the start of study or control treatment for the healing phase. For TEAEs in the maintenance phase, the analyses listed below shall be performed for each treatment group. TEAEs shall be reported using MedDRA terminology and summarized using the Preferred Term (PT) and System Organ Class (SOC) of the MedDRA.

- Aggregation of frequencies of all TEAEs
- Aggregation of frequencies of TEAEs related to the study drug
- Aggregation of frequencies of all TEAEs by severity
- Aggregation of frequencies of TEAEs related to the study drug
- Aggregation of frequencies of TEAEs leading to discontinuation of study treatment
- Aggregation of frequencies of serious TEAEs

Frequency tables will be prepared for the incidences of adverse events and severe hypoglycemia after the first administration of the study drug or comparative drug administration in the “safety population” in each treatment group.

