## 6.0 STUDY DESIGN AND DESCRIPTION

### 6.1 Study Design

#### <Study design>

This is a randomized, open-label, two-way crossover study which aims to examine the patient preference for treatment with once-weekly dosing of DPP-4 inhibitor trelagliptin versus daily dosing of DPP-4 inhibitor alogliptin among the patients with type 2 diabetes mellitus who are being treated with daily dosing of DPP-4 inhibitor.

After obtaining the consent, the subjects who are judged eligible as a result of eligibility check will be randomized either to trelagliptin preceding group (T-A group) or alogliptin preceding group (A-T group).

Planned number of subjects is 60 in total.

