#### <Treatment>

Trelagliptin preceding group (T-A group):

The subjects receive 100 mg of trelagliptin once a week for 8 weeks and then 25 mg of alogliptin once a day for 8 weeks.

Alogliptin preceding group (A-T group)

The subjects receive 25 mg of alogliptin once a day for 8 weeks and then 100 mg of trelagliptin once a week for 8 weeks.

The outline of the clinical research design is shown in Figure 6.a.

See the appendix for schedules of tests, observations, and assessments.

[figure not shown]

Figure 6.a Outline of Clinical Research Design

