6. SAFETY EVALUATION

6.1. Brief Summary of Adverse Events (TEAE)

Analysis Set: Safety Analysis Set

Analysis Variables: TEAE

- 1) All of the TEAEs
- 2) TEAEs Related to Study Drug
- 3) TEAEs by Severity
- 4) TEAEs Related to Study Drug by Severity
- 5) TEAEs Leading to Discontinuation of Study Drug
- 6) Serious TEAEs
- 7) Serious TEAEs Related to Study Drug

8) Serious TEAEs Leading to Discontinuation of Study Drug

9) TEAEs Leading to Death

Analysis Methods: The following analyses are performed on TEAEs.

(1) Calculate the number of subjects and Proportions (%) by Study Drug.

Incidence rates will be calculated as following.

[Frequency of Subjects]

· Frequency by Severity

Subjects with one or more adverse events within a level of MedDRA term is counted only once in that level using the most severe incident. The denominator when calculating the incidence of adverse events is the number of subjects of safety analysis set.

· Analyses Other Than the Above

Subjects with one or more adverse events within a level of MedDRA term is counted only once for that MedDRA term.

The denominator when calculating the incidence of adverse events is the number of subjects of safety analysis set.

(2) For TEAE described in the CRF, prepare a replacement table for SOP and PT. SOC's will be sorted in alphabetical order, then PT's will be sorted in frequency order.

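### Protocol 13.1.4 defines and tabulates TEAEs by phases this crossover does not have and by sequence group; the SAP tabulates by drug but lacks a TEAE definition, an attribution rule and exposure-based denominators

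*Protocol*

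**What the plan says.** **Definition and scope.** Protocol 13.1.4 gives the definition: "A treatment-emergent AE (TEAE) is defined as any AE occurring after the start of study or control treatment for the healing phase". The next sentence sets the scope of the tables: "For TEAEs in the maintenance phase, the analyses listed below shall be performed for each treatment group". The section closes with a separate plan for frequency tables, again per treatment group, of "incidences of adverse events and severe hypoglycemia after the first administration of the study drug or comparative drug administration".

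**Design.** Protocol 6.1 describes two consecutive 8-week periods. For the sequence that starts with trelagliptin: "The subjects receive 100 mg of trelagliptin once a week for 8 weeks and then 25 mg of alogliptin once a day for 8 weeks". The A-T group has the reverse order. No washout is described.

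**SAP.** SAP 6.1 reads: "Calculate the number of subjects and Proportions (%) by Study Drug". SAP 6.2 is also by study drug. Both take the number of subjects in the safety analysis set as denominator, and SAP 2 defines that set as anyone with at least one dose, without splitting by drug. SAP 1 spells out the abbreviation TEAE and goes no further. The time windows in SAP 3.8 cover HbA1c, DTSQ and compliance, not adverse events.

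**Collection.** Protocol 10.2.1.1 starts AE collection at the first dose and adds: "Routine collection of AEs will continue until VISIT 3". Appendix A also has an AE entry in the discontinuation column, where the acceptable range runs to 14 days after the last dose.

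**The concern.** Adverse events are a named endpoint (Protocol 5.2.3), and Protocol 13.0 gives the analysis to personnel independent of the sponsor, who must work from the written text. That text gives them two specifications that do not agree. The protocol's rests on phases that appear nowhere else in either document. The SAP's is by drug, which suits a crossover, but it leaves open which events count as treatment-emergent, which drug an event near the switch belongs to, and how many subjects were at risk on each drug. At stake are whether the safety tables can compare the two drugs and whether two analysts would produce the same counts and percentages. The trial is open-label, so these rules are better fixed in writing than left to discretion.

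**Working it through.** The plan states no AE rate or safety precision, so there is no figure of its own to reproduce. All event rates below are assumptions.

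**1. Phases.** The protocol design has Week 0, a switch at Week 8 and the end at Week 16 (Protocol 6.1, Appendix A). No healing or maintenance phase can be mapped onto it. SAP section 6 has no phase wording.

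**2. Meaning of treatment group.** Protocol 6.1 randomizes to T-A or A-T. SAP 5.1.1 uses T-A and A-T as the rows of its 2×2 table, and SAP 5.2.1 speaks of combining treatment groups. The sequence reading is therefore well supported, and the protocol's table differs from the SAP's.

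**3. What a sequence table can show.** Let pT and pA be the probabilities of at least one event in 8 weeks on trelagliptin and alogliptin. For completers, with independent periods and rates that depend only on the drug:

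P(any event in 16 weeks) = 1 − (1 − pT)(1 − pA)

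The expression is the same for T-A and A-T.

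| Assumed pT, pA | Difference by drug | Each sequence group | Difference by sequence |
|---|---|---|---|
| 10%, 5% | 5 points | 1 − 0.90 × 0.95 = 14.5% | 0 |
| 20%, 10% | 10 points | 1 − 0.80 × 0.90 = 28% | 0 |
| 30%, 10% | 20 points | 1 − 0.70 × 0.90 = 37% | 0 |
| 40%, 10% | 30 points | 1 − 0.60 × 0.90 = 46% | 0 |

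**4. Attribution at the switch.** Visit 2 is allowed on Day 49 to 63 around a nominal Day 56 (SAP 3.8, Appendix A). A cut at nominal Day 56 and a cut at the actual first dose of the second drug can therefore disagree over at most 63 − 56 = 7 or 56 − 49 = 7 days per subject. That is 7 / 112 = 6.25% of the nominal 16 weeks.

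**5. Denominator.** The safety set is at most 60. The plan assumes 10% discontinuation (Protocol 13.3), so 0.10 × 60 = 6 subjects. Suppose all six stop before the switch:

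- 3 in each sequence: each drug is taken by 60 − 3 = 57.
- All 6 in one sequence: that sequence's second drug is taken by 60 − 6 = 54.

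Six subjects with an event on that drug are 6/60 = 10.0% on the SAP's denominator, against 6/57 = 10.5% or 6/54 = 11.1% of those exposed. With no early discontinuation the two denominators agree.

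**6. End of collection.** Protocol 10.2.1.1 stops at Visit 3. Appendix A provides a discontinuation assessment, to be done as far as possible. Neither place says when AE collection ends for a subject who stops early.

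**The case against.** The strongest reply is that the SAP governs. Protocol 13.1 leaves detailed definitions and methods to it, and SAP section 6 plans by-drug tables on the safety set with no phase restriction. AEs are collected from the first dose, so nearly everything collected is treatment-emergent anyway. Onset dates are defined and recorded (Protocol 10.1.7, 10.2.1.2), and worsening after a change of study drug is entered as a new AE (Protocol 10.1.2). With no washout, the onset date points to one drug for most events. AEs are an additional endpoint, tabulated descriptively.

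Most of this stands, and it rules out several stronger readings:

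- *The TEAE tables will be empty.* This follows only from a literal reading of the maintenance-phase sentence. The closing sentence of 13.1.4 and SAP section 6 carry no such restriction.
- *The safety endpoint is itself misdefined.* Protocol 5.2.3 names it simply as adverse events. The fault is in the analysis definition.
- *The sequence tables are worthless, or the by-drug tables arbitrary throughout.* The former still show overall 16-week incidence. In the latter, doubt about attribution is confined to events at or near the switch.
- *Appendix A contradicts 10.2.1.1.* The discontinuation column can be read as a supplement for subjects who never reach Visit 3, and its 14 days are a visit range, not a stated AE window. It needs reconciling, no more.

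The reply does not supply what is missing. The SAP was given the task of detailed definition and does not define a TEAE. The obvious onset-date rule is not written down, and the stated denominator is not the number exposed to each drug. The protocol text also remains operative and in conflict with the SAP.

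**Conclusion.** The point holds in this limited form. Protocol 13.1.4 contains a TEAE definition and a table restriction that do not fit this trial, and its sequence-group layout conflicts with the SAP's by-drug layout. The sequence layout has an expected difference of 0 whatever the drug difference, given completers, independent periods and rates that depend only on the drug; early discontinuers would disturb this slightly. The SAP tables can be produced, with two modest defects: an unwritten attribution rule, bearing on at most 7 days either side of nominal Day 56 when the nominal and actual-dose cuts are compared, and a denominator that lowers by-drug percentages by about 0.5 to 1.1 points in the six-event example, if 3 to 6 of 60 subjects never receive the drug. The primary preference analysis and the sample size are unaffected. It should be corrected because AEs are a named endpoint and the correction is only wording, not because the safety data would be lost.

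**What to change.** **Protocol 13.1.4.** Delete the healing and maintenance wording. Define a TEAE as an AE with onset on or after the first dose of study drug. Change the tables to by study drug, to match SAP section 6.

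**SAP section 6.** It is already by drug and has no phase wording to remove. Add:

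- the same TEAE definition;
- an attribution rule by onset date: events before the actual first dose of the second drug go to the first drug, and events from that dose onward go to the second;
- for each drug, a denominator of subjects who received at least one dose of that drug.

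**Both.** Reconcile the end of AE collection for discontinuers between Protocol 10.2.1.1 and Appendix A. While aligning the sections, settle whether the severe hypoglycemia table planned in 13.1.4 belongs in the SAP, which does not list it.

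**Cost.** Wording in two documents. AE onset dates are already recorded. The date of the first dose of the second drug must be available: the drug details that Protocol 8.2 lists for the CRF do not mention dosing dates, so this should be confirmed.
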